7.9 ANALYSIS OF COVID19 IMPACT

There is currently an outbreak of respiratory disease, COVID-19 worldwide which has impacted the conduct of this trial. This public health emergency has raised more difficulties for patients to meet protocol-specified procedures, including administering or using the investigational product or adhering to protocol-mandated visits and laboratory/diagnostic testing. Site personnel or trial subjects are also under the risk to get infection with COVID-19.

Consequently, there are unavoidable protocol deviations due to COVID-19 illness and/or COVID-19 public and individual health control measures. To assess the impact on patients' safety and drug efficacy in this trial, the following analyses are planned:

Disposition and iPD:

Frequency of the patient with missing visits or early discontinuation due to COVID-19 will be listed. iPDs related to COVID-19 will be also listed if any.

Identification of SARS-CoV-2 infections

Proprietary confidential information © 2021 Boehringer Ingelheim International GmbH or one or more of its affiliated companies
If patients get SARS-CoV-2 infection while on treatment with study drug, AE frequency analysis for subgroup of subjects with SARS-CoV-2 infection while on treatment with study drug will be provided, based on the narrow BICMQ SARS-CoV-2 infections..

AE based on the periods of COVID-19 disruption

- Overall summary of AEs
- AEs by SOC and PT
- AEs leading to d/c by SOC and PT
- SAEs by SOC and PT

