6. INVESTIGATIONAL PLAN

6.1 VISIT SCHEDULE

All patients are to adhere to the visit schedule as specified in the [Flowchart](#). Each visit date (With its window) up to EoT is to be counted from Visit 2 at Day 1 (first trial drug administration day). If any of these visits has to be rescheduled, the date of subsequent visit should be calculated from Day 1.

EoT refers to the End of Treatment visit at week 12 (or earlier if a patient terminates study drug before week 12).

For patients not rolling over to OLE trial, FUP1 refers to Follow-up visit 1 which will be scheduled 8 weeks after last study drug administration. EoS refers to the End of Study visit which will be scheduled 16 weeks after last study drug administration (after REP period).

For patients rolling over to OLE trial, EoT and EoS dates will be the same. These patients will not undergo the safety follow-up period (i.e will not do FUP1 and EoS visits) because they will be followed in the OLE trial. For these patients EoT visit of this trial and first visit of the OLE trial should occur the same day.

Additional visits for the purpose of re-testing of laboratory parameters or AE monitoring may be included as deemed necessary by the investigator.

In exceptional cases, if standard visits at the trial sites are impossible because of COVID-19 related safety risks, the investigator must assess the risk-benefit for each individual patient and may decide to perform a visit remotely if this is in the best interests of the patient and if agreed with the sponsor.

All COVID-19 related deviations from the original schedule of visits and procedures will be documented and the implications considered for the analysis of the trial data.

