6. GENERAL ANALYSIS DEFINITIONS

6.1 TREATMENT(S)

For basic study information on the treatment to be administered, assignment to treatment, and selection of dose, cf. Section 4 of the CTP.

The study phases are defined relative to randomized dose at Day 1 as below:

Table 6.1: 1 Flow chart of analysis phases of the study according to randomized treatment

Study analysis phase	Description	Start (included)	End (included)
Screening phase	Screening	Earliest of (Date of informed consent, first screening procedure)	Date/time of start of the first study dose minus 1 minute.
Loading treatment phase	On-treatment period	Date/time of start of the first study loading dose (Day 1)	Earlier of: i) Date/time of start of the first maintenance dose minus 1 minute; or, ii) Date of end of last loading dose + 112 days at 11:59 p.m. if patient early discontinued study treatment before the first maintenance dose
Maintenance treatment phase (primary analysis at week 12)		Date/time of start of the first study maintenance dose (if applicable)	Earlier of : i) Date/time of start of the first dose in the extension trial 1368.67; or, ii) Date of end of last maintenance dose + 112 days at 11:59 p.m, iii) cut-off date for primary analysis.
Follow-up phase ¹ (if applicable)	Off-treatment period (if applicable)	Date of end of last study dose + 113 days at 0:00 a.m.	Latest of: i) Date of EOS visit; ii) last contact date on trial termination page at 11:59 p.m. iii) Date/time of start of first dose in the extension trial 1368.67;

Dates are defined individually per patient. If more than one date is associated with a specific visit, measurements associated with a specific date are assigned to a study analysis phase according to the rules specified in the table. An analysis phase will not extend beyond the start date of the following phase.

¹ The off-treatment period (i.e. Follow-up phase) only exists if the date of EoS visit or the last contact date is after the date of end of last administration + 112 days.

Treatment groups for the analysis phases according to the randomized/actual treatment on Day 1 (see [Table 6.1: 1](#)) will be labelled as follows:

Proprietary confidential information © 2021 Boehringer Ingelheim International GmbH or one or more of its affiliated companies

- **"Placebo"** (i.e. randomized to receive /actual received Placebo)
- **"Speso"** (i.e. randomized to receive /actual received Spesolimab)
- **"Overall Total"**(across treatments), where appropriate.

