The following standard descriptive statistical parameters will be displayed in summary tables of continuous variables:

Proprietary confidential information © 2021 Boehringer Ingelheim International GmbH or one or more of its affiliated companies

N	number of non-missing observations
Mean	arithmetic mean
SD	standard deviation
Min	minimum
Q1	lower quartile
Median	median
Q3	upper quartile
Max	maximum

For PK analyte concentrations, the following descriptive statistics will additionally be calculated: variables:

CV:	arithmetic coefficient of variation
gMean:	geometric mean
gCV:	geometric coefficient of variation

The data format for descriptive statistics of concentrations will be identical with the data format of the respective concentrations.

Statistical parameters will be displayed to a defined number of decimal places as specified in the BI guideline "Standards for Reporting of Clinical Trials and Project Summaries." ([10](#))

Tabulations of frequencies for categorical data will include all possible categories and will display the number of observations in a category as well as the percentage (%) relative to the respective treatment. Percentages will be rounded to one decimal place. The category missing will be displayed if and only if there actually are missing values. Percentages will be based on all patients in the respective patient set whether they have non-missing values or not.

Disposition of the patient population participating in the trial will be summarized by the presentation of the frequency of patients screened, randomized, screened but not randomized, randomized but not treated, randomized and treated, who completed randomized medication, who withdrew from the trial before EOT visit, by reason, who were prematurely discontinued from trial medication, by reason, who received rescue therapy for HS worsening and who entered the extension trial 1368.67.

The frequency of patients with iPDs, also summarized by whether or not the iPD led to exclusion from the PPS, will be presented.

The frequency of patients in each of the different analysis sets will also be presented.

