7.7 EXTENT OF EXPOSURE

An overall table will be summarized for the entire maintenance treatment period. The number of subjects who received a dose of trial drug will be tabulated. Treatment exposure will be assessed as the total dose of randomized treatment [mg] administered for the loading stage, the maintenance stage, as well as the overall dose across the two stages, which will be summarised by descriptive statistics (N, mean, SD, minimum, median, maximum). The total duration of exposure [days] will also be displayed.

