7.8 SAFETY ANALYSIS

All safety analyses will be performed on the safety analysis set.

All safety analyses will be performed following BI standards. No hypothesis testing is planned. OC-IR and OR methods will be used for safety reporting. All safety analysis will be performed for on-treatment period.

AE and possibly clinically significant laboratory abnormalities will be analyzed under OR (as defined in [Section 6.6.3](#)); the safety data by visit, i.e., laboratory, vital signs and local tolerability, will be analysed under OC-IR (as defined in [Section 6.6.3](#)).

As the onset time of an AE will not be collected in the trial, any AE which occurs on the same day as a treatment dose will be assigned to the “post treatment”. For safety assessments by visits, if time is not collected, data on the same day of a treatment dose will be treated to be “prior treatment” except for scheduled local tolerability and post-dose vital signs assessments.

Off-treatment data will be listed only.

Additional analyses on AE will be also included:

AE within loading stage

Proprietary confidential information © 2021 Boehringer Ingelheim International GmbH or one or more of its affiliated companies
For AE, the additional safety tables for loading dose stage will be produced by grouping patients based on their loading doses (1200 mg, Placebo) using SAF. The outputs will include on-treatment data up to the first maintenance dose at or post week 4. If patients discontinued from treatment prior to receiving first maintenance dose, then the safety data up to the date of last loading dose + 112 days will be included.

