7.8.1 Adverse Events

AEs will be coded with the most recent version of MedDRA.

The analyses of AEs will be descriptive in nature. All analyses of AEs will be based on the number of patients with AEs and not on the number of AEs. System organ classes (if applicable) will be sorted according to the standard sort order specified by the EMA, preferred terms (if applicable) will be sorted by total frequency (within system organ class).

For details on summarization of AE data, please refer to "Handling and summarization of adverse event data for clinical trial reports and integrated summaries" (15) and "Handling of missing and incomplete AE dates" (4).

The analysis of AEs will be based on the concept of treatment-emergent AEs. This means that all AEs will be assigned to the screening period, loading treatment phase, maintenance period (i.e. maintenance treatment phase plus REP) or off-treatment period (i.e. follow up) as defined in Section 6.1. Since only the start date of an AE is collected (without start time), any AE occurrence on the same day as the first Spesolimab administration will be assigned to the on-treatment phase.

An overall summary of AEs will be presented by treatment. This overall summary will include summary statistics for the class of other significant AEs (sponsor definition based on ICH E3) and for the class of AESIs.

The following is considered an AESI in this trial:

Systemic hypersensitivity including infusion reaction and anaphylactic reaction

Severe infections (according to RCTC grading)

Opportunistic and mycobacterium tuberculosis infections

Hepatic injury

A hepatic injury is defined by the following alterations of hepatic laboratory parameters:

- an elevation of AST (Aspartate Aminotransferase) and/or ALT (Alanine Aminotransferase) ≥ 3 fold ULN combined with an elevation of total bilirubin ≥ 2 fold ULN measured in the same blood draw sample, or in samples drawn within 30 days of each other
OR
- aminotransferase (ALT, and/or AST) elevations ≥ 10 fold ULN.

Proprietary confidential information © 2021 Boehringer Ingelheim International GmbH or one or more of its affiliated companies
 In addition, user defined adverse event concepts (UDAEC) identified through specific search criteria will be reported separately (see [Table 7.8.1:1](#)).

Table 7.8.1: 1 Project MEDDRA search criteria for User Defined Adverse Events Concepts

User-defined AE category		
	Label	Description

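### SAP 7.9's adverse event tables by COVID-19 period are crude patient percentages without patient-time, so comparing periods mixes time at risk with any effect of disruption

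*SAP*

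**What the plan says.** SAP 7.9 introduces its COVID-19 section with a purpose: "To assess the impact on patients' safety and drug efficacy in this trial, the following analyses are planned". One of its three components is headed "AE based on the periods of COVID-19 disruption" and names four outputs: an overall AE summary, AEs by system organ class and preferred term, AEs leading to discontinuation, and serious AEs. The available text of that section gives no period dates, denominator or rate.

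The general rules therefore apply:

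- **Unit of analysis (SAP 7.8.1):** "All analyses of AEs will be based on the number of patients with AEs and not on the number of AEs".
- **Denominator (SAP 7, General Remarks):** "Percentages will be based on all patients in the respective patient set whether they have non-missing values or not".
- **Exposure (SAP 7.7):** "The total duration of exposure [days] will also be displayed". This is a total. It is not split by pandemic period and is not linked to AEs.
- **Observation window (SAP 7.8):** "All safety analysis will be performed for on-treatment period". Under SAP Table 6.1: 1 this period can end at the first extension-trial dose, at "Date of end of last maintenance dose + 112 days at 11:59 p.m", or at the cut-off date for the primary analysis.

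On visit conduct, Protocol 6.1 says that in exceptional cases the investigator "may decide to perform a visit remotely if this is in the best interests of the patient and if agreed with the sponsor". Protocol 4.1.4 allows dosing at home during the pandemic.

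**The concern.** A table of AEs by period, offered as evidence on the pandemic's impact, invites the reader to compare periods. The percentage with at least one AE in a period depends on the AE rate and on how long patients were observed in that period. Screening is competitive across sites (Protocol 3.3), so patients will not all start together. They will contribute unequal time to each period, and some may contribute none.

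Two wrong conclusions are then possible. A short disruption period would look safer with no change in the AE rate, and a real increase during disruption could still appear as a lower percentage.

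Detection may also differ. Local tolerability reactions, and clinically relevant examination, ECG and laboratory findings, are reported as AEs. Remote visits or home dosing could plausibly reduce how many are found. A crude count cannot separate fewer events found from less time observed.

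**Working it through.** The documents give no figure to reproduce on this point. The check asks what the planned table would show when the truth is known.

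**Inputs from the documents.** About 45 patients are randomized 2:1 (SAP 3). On-treatment time is about 12 weeks for a patient entering the extension trial. For a patient who completes dosing and does not enter it, the last dose at Week 10 plus 112 days (16 weeks) gives 10 + 16 = 26 weeks.

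**Assumptions not in the documents.** The AE rate, the share of time disrupted, the accrual period and the disruption dates.

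**Step 1: constant rate, no effect of disruption.** Let p be the proportion with an AE over the whole window and f the share of each patient's time that is disrupted. The cumulative hazard is H = −ln(1 − p). The expected percentages are 1 − exp(−fH) during disruption and 1 − exp(−(1 − f)H) outside it. With p = 60%, H = −ln(0.4) = 0.916.

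| Share disrupted | During disruption | Outside disruption |
|---|---|---|
| 10% | 8.8% | 56.2% |
| 25% | 20.5% | 49.7% |
| 50% | 36.8% | 36.8% |

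For the 25% row: 1 − exp(−0.229) = 20.5% and 1 − exp(−0.687) = 49.7%. The rate is the same in both columns.

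**Step 2: other assumptions.** With f = 25% and a 12-week window, values of p from 30% to 70% give 8.5% vs 23.5% up to 26.0% vs 59.5%; p = 50% gives 15.9% vs 40.5%. If that last rate runs for 26 weeks, the figures are 31.3% vs 67.6%. With f = 75% and p = 50% over 12 weeks the order reverses: 40.5% during disruption and 15.9% outside.

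**Step 3: a real effect.** With p = 50%, f = 25% and 12 weeks, doubling the rate during disruption raises that figure from 15.9% to 29.3%. It is still below the 40.5% outside.

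**Step 4: staggered entry.** Simulation: 45 patients, entry uniform over 52 weeks, 12 weeks at risk each, 50% with an AE by 12 weeks, a 13-week calendar window of disruption (about 25% of patient-time), 4,000 repetitions. Each cell gives disruption vs outside.

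| True rate ratio | % of all patients | % of patients with any time in the period | Events per 100 patient-weeks |
|---|---|---|---|
| 1 | 13.6 vs 39.0 | 30.8 vs 39.6 | 5.8 vs 5.8 |
| 2 | 22.3 vs 39.1 | 50.3 vs 39.7 | 11.6 vs 5.8 |

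Patient-time recovers both true ratios. Restricting the denominator to patients with some time in the period helps but does not cure the problem. With a 6-week window and no effect it still gives 22.0% vs 45.5%.

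**The case against.** **The plan does not say that periods will be compared.** SAP 7.9 gives a heading and table names, and AEs are otherwise presented by treatment. Randomized arms share calendar time, and Protocol 7.4 randomizes in blocks, so spesolimab against placebo within a period stays roughly fair. This stands, and it confines the point to the contrast between periods. If all trial time fell in one period there would be no contrast to distort.

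**Rates are not excluded.** Counting patients rather than events is compatible with a first-event rate. SAP 7.8 and 7.8.1 defer to sponsor standards and an AE guideline that are not available here, and some SAP sections are redacted. This also stands: the point can only be that no patient-time by period appears in the available text.

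**The illustration is stylised.** Step 1 gives every patient the same split of time. If each patient fell wholly inside one period and denominators counted only those at risk, both periods would show 60%. That is correct, but the SAP's stated denominator is the whole set. With a quarter of patients wholly in disruption, that gives 0.25 × 60% = 15% vs 0.75 × 60% = 45%.

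**Detection is partly covered elsewhere.** SAP 7.9 also lists missed visits and discontinuations due to COVID-19. Protocol 6.1 limits remote visits to exceptional cases and has COVID-related deviations documented. Local tolerability is also collected by retrospective questioning. The documents do not say which assessments a remote visit omits, so reduced detection is a possibility rather than a finding.

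**A reader might go further and infer that the percentages say nothing about disruption.** The documents and the arithmetic do not support that. In Step 3 a doubled rate moves the figure from 15.9% to 29.3%. The effect is confounded with time, not absent.

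**Conclusion.** The concern holds as a limited, low-consequence point. Followed as written, the tables by COVID-19 period are crude patient percentages, and any comparison between periods mixes time at risk with any effect of disruption.

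Size and direction cannot be fixed. The available text does not define the periods, and on-treatment time runs from about 12 to about 26 weeks per patient. The 20.5% vs 49.7% is an illustration that rests on a constant rate, 60% with an AE over the window and a quarter of each patient's time disrupted. A larger disrupted share would reverse it.

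A reader might also infer that the trial's main safety comparison or its efficacy result is compromised. Neither follows. The comparison of arms within a period is not materially affected, safety analyses are descriptive without hypothesis testing (SAP 7.8), and the primary endpoint does not use these tables.

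**What to change.** In SAP 7.9:

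1. Define the disruption periods by calendar date, by country if they differ. Without dates the tables cannot be programmed.
2. Assign each AE to a period by its start date.
3. For each period and arm, show the number of patients with on-treatment time in that period and the patient-time they contribute.
4. Add an exposure-adjusted first-event rate for the overall AE row, with time counted to the first event in the period. This keeps the patient as the unit of analysis.
5. For serious AEs and AEs leading to discontinuation, pool the arms or give counts beside patient-time.
6. Report the share of visits done remotely in each period, so that lower reporting can be considered alongside lower occurrence.

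The cost is a few columns built from AE start dates, dosing dates and visit dates already collected. Visit mode should be recoverable from the COVID-related deviations that Protocol 6.1 requires to be documented.

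The downside is imprecision. With 15 placebo patients, 84 days each and 10% of time disrupted, patient-time is 15 × 84 × 0.10 = 126 days, or about 0.35 patient-years. A single event would then read as roughly 290 per 100 patient-years. That is why the sparse rows should not carry rates by arm, and why the tables should remain descriptive.

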7.10 HANDLING OF DMC ANALYSES

A fully external DMC, independent of the trial and project teams, will be set-up to review all available un-blinded safety data as well as selected efficacy data at regular intervals following first-patient-in. A separate DMC SAP which describes the analyses required for assessment by the DMC will be produced. Further details are provided in a DMC charter.

7.11 OTHERS

7.11.1 Biomarkers

The following biomarkers will be analysed and reported as a part of the CTR:

- HS-CRP

Results on other biomarkers (e.g. RNA expression, serum and plasma biomarkers) may or may not be reported in the CTR, depending e.g. on the availability of the data. In case they are reported outside the CTR the analysis will be defined in a separate document (otherwise the analysis will be described in the CTR).

For the analysis of biomarkers, log transformed data will be used where deemed necessary.

7.11.2 Immunogenicity

The ADA status and titer as well as frequency of patients with ADA to Spesolimab will be presented by visit. Descriptive statistics of ADA titer (for ADA positive patients, when available) will be provided by visit. The number of subjects with ADA status positive/negative at any time will also be presented. ADA parameters (e.g. treatment-induced ADA positive subjects, transient ADA response and persistent ADA response) will also be presented by visit and cumulatively for the overall study duration. Further exploratory assessments of the ADA data will be performed once data is available and these will be described, if done, in the CTR.

Further analyses based on ADA data may be performed such as

- efficacy-based subgroup analysis as described in [Section 7.4.2](#) for the 2 groups
- ADA positive and ADA negative subjects (at Week 12), or

Proprietary confidential information © 2021 Boehringer Ingelheim International GmbH or one or more of its affiliated companies

- NAb positive and NAb negative subjects (at Week 12)
- Safety-based subgroup analysis (using e.g. hypersensitivity safety events) for the 2 groups
 - ADA positive and ADA negative subjects (at any time), or
 - NAb positive and NAb negative subjects (at any time), or before ADA development (including subjects with events either before their first ADA positive sample or without ADA positive sample throughout) and after ADA development (including subjects with events from the time point of their first ADA positive sample onwards). This approach takes into account the time when ADA actually developed and when the safety event occurred in relationship to ADA.

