3 X^c is a complete physical examination. X^t is a targeted physical examination. See [section 5.2.1](#).

4 Measurements of vital signs should precede blood sampling to avoid the impact of blood sampling on the vital measurements at all dosing visits. Additional assessments of vital signs should be performed at 10 minutes post-dose for s.c administrations and 5 minutes and 1 hour post dose for i.v. administrations.

5 Women of childbearing potential only. A serum pregnancy test will be performed at screening. Urine pregnancy tests will be performed at all other visits indicated in the [Flowchart](#). In case of a positive urine pregnancy test, a serum pregnancy test will be done. Urine pregnancy testing should be done prior to administration of study drug. Study drug should only be administered in case of a negative test result. More frequent testing should be done if required by the local regulation or per investigator judgment.

6 It is preferred but patients do not have to be fasted for the blood sampling for the safety laboratory. At visits with study drug administration this should be done prior to the study drug administration. See [Table 5.2.3:2](#) for detailed information of the tests. If needed, safety lab samples for Visit 2 can be drawn within 48 hours before the actual visit date.

7 Infection Testing: At screening and at EoT visit. See section safety laboratory parameters for complete list of testing required (see [Table 5.2.3:1](#)).

8 Patients who terminate study drug early should do the EoT visit as soon as possible. These patients will then do FUP1 and EoS visits, 8 and 16 weeks after last study drug administration respectively.

9 At study visits with study drug administration, pre-dose PK/ADA/Nab samples will be obtained approximately within 1 hour prior to start of i.v. infusion or s.c. injection.

10 Desoxyribonucleid Acid (DNA) banking sample is optional. This sampling is only possible if the patient agreed by signing a separate informed consent. For details please see [Section 5.5](#).

11 At selected sites, where ultrasound is available, it is required to do ultrasound lesion evaluation and to guide biopsies. At sites without ultrasound capabilities, biopsies will be done without ultrasound guidance.

12 At Screening, the C-SSRS baseline/screening scale will be completed. At all subsequent visits the “Since last visit” scale will be completed.

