There were no relevant changes compared to placebo for laboratory safety, including clinical chemistry, haematology, coagulation parameters, and urinalysis. No clinically relevant changes were observed in 12-lead ECGs, vital signs, and cardio-monitoring.

PK analysis showed that exposure (AUC_{0-tz} and C_{max}) to spesolimab increased with increasing dose in an approximately dose-proportional manner from 0.3 to 10 mg/kg.

The effective half-life of spesolimab is approximately 4 weeks in the linear dose range. Overall, PK data so far suggests target-mediated drug disposition (TMDD) kinetics for

spesolimab. Anti-drug antibodies (ADA) were detected in 8 patients, 3 of those had pre-existing levels. Pharmacodynamic effects in this FIH Single Rising Dose trial [[c03361085](#)] were assessed by indirect target engagement (ITE) of IL36R by spesolimab using an ex-vivo whole blood stimulation assay. Preliminary analyses indicate that $\geq 94\%$ peripheral IL36R receptor occupancy is achieved with doses $\geq 0.05\text{mg/kg}$ from 30 minutes post infusion to 10 weeks.

In a multiple rising dose trial, spesolimab or placebo have been administered to healthy volunteers at multiple ascending i.v. doses of 3, 6, 10 and 20 mg/kg given qw for 4 weeks (i.e. 4 administrations) or a single dose of 20mg/kg (8 subjects each, 3:1 on active or PBO). Overall, spesolimab was well tolerated. There were no dose dependent AEs, AEs considered to be dose limiting and no SAEs. In all cases the AEs were of mild or moderate intensity. Furthermore, there were no clinically relevant abnormalities on treatment with spesolimab with respect to safety laboratory, vital signs, or ECGs as assessed by a central reader. For further details and most recent results refer to the current Investigator's Brochure (IB) [[c03320877-09](#)].

Studies in Patients

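### In the optional before/after ADA safety split, a patient already ADA-positive before the first dose has every analysed event counted as following ADA development

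*SAP*

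**What the plan says.** SAP 7.11.2 introduces the analysis as optional: "Further analyses based on ADA data may be performed such as". Two kinds of safety grouping are then listed.

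- A status comparison, "ADA positive and ADA negative subjects (at any time), or" the same for NAb.
- A time split. One side is "before ADA development (including subjects with events either before their first ADA positive sample or without ADA positive sample throughout". The other is "after ADA development (including subjects with events from the time point of their first ADA positive sample onwards".

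The stated reason for the time split is "This approach takes into account the time when ADA actually developed and when the safety event occurred in relationship to ADA".

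Earlier in the same section, treatment-induced ADA appears among the descriptive outputs: "ADA parameters (e.g. treatment-induced ADA positive subjects, transient ADA response and persistent ADA response) will also be presented by visit". That category is not used to form either safety grouping.

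On sampling, footnote 9 of the protocol Flowchart says that at dosing visits "pre-dose PK/ADA/Nab samples will be obtained approximately within 1 hour prior to start of i.v. infusion or s.c. injection". Protocol Table 10.1:1 lists Visit 2, Day 1, as sample 1 for PK, ADA and Nab. On prior experience, protocol 1.2.1 states: "Anti-drug antibodies (ADA) were detected in 8 patients, 3 of those had pre-existing levels".

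**The concern.** Antibody found before the first dose did not develop on trial treatment. The time split nevertheless starts the later period at the first positive sample, whichever sample that is. For a patient positive at Visit 2, that start coincides with the start of treatment.

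The section gives hypersensitivity as its example outcome, and systemic hypersensitivity is an adverse event of special interest in this trial. The later group would mix reactions in patients whose antibodies arose on spesolimab with events in patients who carried reactivity in from the start. With very few ADA-positive patients expected, one or two such cases could change how the table reads.

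**Working it through.** **Classification under the written rule.** The documents give no figure for this analysis, so there is nothing to reproduce. The check applies the rule as written.

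1. The first scheduled ADA sample is pre-dose on Day 1 (protocol Table 10.1:1 and Flowchart footnote 9).
2. All safety analyses cover the on-treatment period only (SAP 7.8). An adverse event on the day of first dosing counts as on-treatment, because onset times are not collected (SAP 7.8.1). Every analysed event therefore falls on Day 1 or later.
3. An event is 'after' if its day is on or later than the day of the first positive sample, and 'before' otherwise.

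The latest on-treatment day for a fully dosed patient is the last dose on Day 71 plus 112 days, which is Day 183. Event days 1, 2, 8, 15, 29, 43, 85 and 183 are classed as follows:

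| First positive ADA sample | Events classed 'before' | Events classed 'after' |
|---|---|---|
| Visit 2, pre-dose (Day 1) | none | all eight |
| Visit 5 (Day 29) | Days 1, 2, 8, 15 | Days 29, 43, 85, 183 |
| Never | all eight | none |

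The middle and last rows behave as the split intends. The first row does not: no analysed event can be 'before'.

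**How many patients this might touch.** Protocol 1.2.1 gives 8 ADA-positive subjects, 3 of them with pre-existing levels, but no denominator. The context is the single rising dose trial, which had 59 subjects on spesolimab and 78 on spesolimab or placebo. Both are tried here as assumed denominators, with 30 spesolimab patients planned.

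| Quantity | Formula | Denominator 59 | Denominator 78 |
|---|---|---|---|
| Pre-existing ADA expected | 30 × 3/d | 1.5 | 1.2 |
| Chance of at least one | 1 − (1 − 3/d)^30 | 0.79 | 0.69 |
| ADA-positive at any time, expected | 30 × 8/d | 4.1 | 3.1 |
| ADA-positive without the pre-existing | 30 × 5/d | 2.5 | 1.9 |

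So roughly 1 to 2 of about 3 to 4 ADA-positive patients in the active arm would be placed wrongly in the time split.

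**The case against.** The strongest reply is that this is one optional example in an exploratory section, with no hypothesis test and no link to the primary endpoint. That is correct and limits the importance of the point. It does not make the rule fit its stated purpose.

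The section also tabulates ADA status and titre by visit and treatment-induced positives, and SAP 7 lists individual values. A careful reader could therefore find the baseline-positive patients. The table built from the split would still misplace them.

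For the comparison by ADA status at any time, the objection largely succeeds. That comparison asks about the presence of antibody, and pre-existing antibody is a legitimate part of that question. The error is firm only for the time split.

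The prior data are thin. They come from single doses in healthy volunteers, whereas this trial gives repeated doses to patients. The share of positives that are pre-existing depends on how many are induced, and a single-dose study does not settle that.

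Two stronger readings are tempting. A reader might infer that, because the first scheduled post-baseline ADA sample is Day 15, any earlier event classed as 'after' must come from a baseline-positive patient. The protocol does not support this: section 4.2.1.1 calls for an ADA sample at a systemic hypersensitivity or infusion reaction, so a first positive can arise earlier, and Visit 4 has a window of ±1 day. A reader might also express the mixing as a share of patient-time. That would need an assumed spread of first positives, and SAP 7.8.1 bases adverse event analyses on numbers of patients.

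Finally, parts of the SAP are redacted, so a definition elsewhere cannot be excluded. SAP 7.11.2 refers to none.

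**Conclusion.** The point holds for the before/after split. As written, it classes all analysed events of a baseline-positive patient as following ADA development, contrary to its own stated aim. This follows from the wording and the sampling schedule and needs no numerical assumption.

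The likely size, about 1 to 2 of 30 spesolimab patients against about 3 to 4 expected positives, is illustrative. It assumes that the single rising dose rates carry over and that the denominator is 59 or 78. The consequence is confined to how ADA-related hypersensitivity is interpreted. The primary result is not affected, and neither are the optional efficacy subgroups, which use ADA or NAb status at Week 12. This is a modest correction to an optional table.

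**What to change.** In SAP 7.11.2, for the before/after split, date ADA development from the first treatment-emergent sample. That is either:

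- for a patient negative at baseline, the first positive post-baseline sample; or
- for a patient positive at baseline, the sample that first shows a pre-specified rise in titre.

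Show baseline-positive patients without such a rise as a separate row. For the ADA and NAb comparisons by status at any time, keep the grouping but display baseline-positive patients separately. Settle the wording and the titre criterion before unblinding, so that the grouping is not chosen with the events in view.

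The cost is a few lines of SAP text and one derived flag from samples already scheduled. The drawback is a smaller 'after' group in an analysis that is already small. If a redacted section already contains such a definition, a cross-reference to it is enough.
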